Title of the study: Rehabilitative Trial With Cerebello-Spinal tDCS in Neurodegenerative Ataxia

NCT number: NCT03120013

Date: January 21, 2016

Standard Protocol Approvals, Registrations, and Patient Consents

Full written informed consent was obtained from all participants according to the Declaration of Helsinki. The study protocol was approved by the local ethics committee (Brescia Hospital), #NP1576 approved 01.21.16. This trial has been registered at ClinicalTrials.gov (NCT03120013).

Primary research questions/classification of evidence

Our primary research question was to determine whether cerebellar anodal tDCS and spinal cathodal tDCS could improve symptoms and modulate cerebello-cerebral connectivity in patients with ataxia, at short and long-term.

Participants

Twenty-one patients with neurodegenerative ataxia, respectively seven patients with spinocerebellar ataxia (SCA) type 2,¹ six with the cerebellar variant of multiple system atrophy (MSA-C),² one with SCA38,³ one with SCA14,⁴ one with Friedreich's ataxia,⁵ one with Ataxia with Oculomotor Apraxia (AOA) type 2,⁶ four with sporadic adult-onset ataxia,⁷ were recruited from the Centre for Ageing Brain and Neurodegenerative Disorders, Neurology Unit, University of Brescia, Italy and entered the study. One patient with MSA-C dropped out from the study during the first round (sham stimulation) and was not considered in the present analysis.

The number of included patients, corrected for possible drop-outs and patients in which a reliable motor cortex could not be elicited, was assessed using a power analysis, from results obtained from previous studies.⁸

Each patient fulfilled current clinical criteria and genetic trait for the specific diagnosis. All enrolled patients shared a cerebellar syndrome and, as assessed by MRI, had quantifiable cerebellar atrophy. For each patient, a review of past medical history, a semi-structured neurological examination and a standardized assessment of cerebellar functions was carried out.

Patients were evaluated free of sedative drugs or sodium- or calcium-channel blockers to avoid any interaction with the presumed neuromodulatory effects of tDCS.

In addition, ten age-matched healthy control subjects were recruited as reference group for TMS parameters.

Study design

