Patients were randomized into two groups: each group received anodal cerebellar tDCS and cathodal spinal tDCS (real tDCS) or sham stimulation for 5 days/week for 2 weeks, in a 1:1 ratio respectively.

At baseline, each patient underwent a clinical evaluation, according to a standardized assessment (see below, clinical assessment), and CBI evaluation using Transcranial Magnetic Stimulation (TMS) (see below, CBI assessment) (pre-stimulation, T0). The same assessments were carried out after two-weeks of either real or sham tDCS (post-stimulation, T1), at one-month (T2) and at three-months follow-up (T3).

After a wash-out period of three months after the last visit (i.e., T3), each patient received the opposite treatment (cross-over phase), and underwent the same standarized assessment as in the first phase, at baseline, at two-weeks post-stimulation, at one-month and at three-months (see **Fig 1**).

Six principal investigators were involved: one performing the clinical evaluation ([name]), one performing CBI at baseline and at follow-up ([name]) and four performing tDCS ([name], [name], [name], [name]). The patient and the examiners performing clinical ratings and TMS protocols were blinded to the type of stimulation.

Clinical assessment

At each time-point, the Scale for the Assessment and Rating of Ataxia (SARA)⁹ and the International Cooperative Ataxia Rating Scale (ICARS)¹⁰ were employed to evaluate cerebellar deficits.

SARA consists of eight items, including gait, stance, sitting, speech disturbance, finger chase, nose-finger test, fast alternating hand movements, and heel-shin slide. The higher the score, the worse is the patient's performance. ICARS is a semiquantitative 100-point scale consisting of 19 items, divided into four weighted sub-scores, namely posture and gait disturbances, limb kinetic function, speech disorder, and oculomotor deficits.

To evaluate finger dexterity and upper limb coordination, four timed trials of the 9-hole peg test (9HPT)¹¹ were performed separately for each hand. The 9HPT is a commonly used test to assess finger dexterity: the patient picks the pegs one at time and puts them in nine holes on a peg board until all holes are filled and then removes them one at a time, as quickly as possible. The total time to complete the task is recorded for each trial and for each separate hand (dominant and non-dominant).

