To assess the effect of tDCS treatment on clinical scores over time we used a two-way repeated measure ANCOVA with TIME (T0, T1, T2 and T3) and TREATMENT (sham vs real stimulation) as within-subjects factors, and the sequence in which stimulation was performed (real-sham vs sham-real) as covariate.

To assess the effect of tDCS treatment on CBI we used a three-way repeated measures ANCOVA with TIME (T0, T1, T2 and T3), ISI (3, 5, 10 ms) and TREATMENT (sham vs real stimulation) as within-subject factors, and the sequence in which stimulation was performed (real-sham vs sham-real) as covariate.

When a significant main effect was reached, *post hoc* tests with Bonferroni correction for multiple comparisons were conducted to analyze group-differences at respective ISIs or time points. Mauchly's test was used to test for assumption of sphericity, while Greenhouse–Geisser epsilon determination was used to correct in case of sphericity violation.

Spearman's rank-order correlations were used to assess associations between the improvement in functional scores, neurophysiological parameters and demographic or clinical characteristics. Statistical analyses were performed using SPSS version 21 (SPSS, Inc., Chicago, IL, USA).

References

6. Moreira M-C, Klur S, Watanabe M, et al. Senataxin, the ortholog of a yeast RNA helicase, is mutant in ataxia-ocular apraxia 2. *Nat Genet*. 2004;36(3):225-227. doi:10.1038/ng1303.

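### The visit-level real-versus-sham tests open on an unnamed main effect, and TIME × TREATMENT is never named, so whether a short-lived effect gets tested depends on the reading

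*Combined protocol and SAP*

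**What the plan says.** The primary research question is whether stimulation "could improve symptoms and modulate cerebello-cerebral connectivity in patients with ataxia, at short and long-term". Study design defines T0 as "pre-stimulation, T0" and places T1 after the two weeks of stimulation, T2 at one month and T3 at three months, in each crossover period.

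Statistical Analyses gives the clinical model as a "two-way repeated measure ANCOVA with TIME (T0, T1, T2 and T3) and TREATMENT (sham vs real stimulation) as within-subjects factors". Its stated purpose is "To assess the effect of tDCS treatment on clinical scores over time". The CBI model is a "three-way repeated measures ANCOVA with TIME (T0, T1, T2 and T3), ISI (3, 5, 10 ms) and TREATMENT (sham vs real stimulation"). Both take sequence as covariate.

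The follow-up rule is conditional. Its trigger is worded "When a significant main effect was reached". What the trigger opens is a further set of comparisons, described as "tests with Bonferroni correction for multiple comparisons were conducted to analyze group-differences at respective ISIs or time points". The rule does not identify the main effect. No treatment-by-time term is named in the document. Alpha, SD, effect size and the size of the Bonferroni family are not given either.

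**The concern.** The question is about a treatment difference that may change over time. In these models the term that carries it is TIME × TREATMENT. The written rule instead makes the visit-level comparisons conditional on a main effect, and there are two to choose from for clinical scores and three for CBI. The candidates behave differently:

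- **TREATMENT** averages the real-minus-sham difference over all four visits, including T0, where stimulation cannot yet have acted. A benefit that fades after T1 is diluted.
- **TIME and ISI** pool real and sham. If either can open the tests, whether treatment is compared depends partly on changes unrelated to treatment.
- **TREATMENT or TIME × TREATMENT**, if that is what was meant, costs little.

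The short-term half of the question is at stake: a real T1 effect might never be tested. Two analysts following the same sentence could also reach different conclusions on the same data.

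**Working it through.** **Inputs from the document.** Twenty-one patients enrolled and one was excluded after dropping out, leaving 20. With sequence in the model the error df is 20 − 2 = 18. There are four visits per period, and T0 is one of the TIME levels. There is no stated power or effect figure to reproduce.

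**Assumed, because the document gives none.** Two-sided alpha 0.05; 10 patients per sequence; residual SD 1 at each visit; patient-by-period SD s = 0, 0.5 or 1; effect 1 residual SD at T1; T1 comparison at 0.05/4. Triplets below are for s = 0/0.5/1.

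**Dilution (no SD needed).** In the TREATMENT main effect, an effect d enters as:
- T1 only: d/4
- full at T1, half at T2, none at T3: (d + d/2)/4 = 0.375d
- T1 and T2: d/2
- T1 to T3: 3d/4
- CBI, one ISI at T1: d/12 (3 ISIs × 4 visits)

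**Noncentral t, df 18, T1-only effect.**
- TREATMENT: noncentrality = 0.25 / √[2(s² + 1/4)/20] = 1.58/1.12/0.71. Chance of significance at 0.05: 32/18/10%.
- T1 comparison alone: noncentrality = 1 / √[2(1 + s²)/20] = 3.16/2.83/2.24. Chance of significance at 0.05/4: 65/53/33%.
- For a sustained effect, TREATMENT has noncentrality 0.75 / √[2(s² + 1/4)/20] = 4.74/3.35/2.12, giving 99/89/52%.

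**Simulation of the whole rule** (10,000 replicates per scenario, sequence as covariate, Greenhouse–Geisser correction; runs agree within about 1 point). Entries are the percentage of trials in which the gate opens and the T1 comparison succeeds.

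| Effect profile | No gate | TREATMENT | TREATMENT or TIME × TREATMENT | TIME × TREATMENT alone |
|---|---|---|---|---|
| T1 only | 65/54/33 | 27/16/9 | 58/47/29 | 48/42/25 |
| Full, half, none | 65/54/33 | 47/29/14 | 62/49/29 | 44/38/24 |
| T1 and T2 | 65/53/33 | 60/40/20 | 65/52/31 | 52/43/27 |
| Sustained | 66/54/33 | 66/52/29 | 66/54/32 | 40/34/21 |

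**Any main effect as gate, T1-only effect.** With no change shared by the two periods, success is 48/37/22%, a loss of about 10–17 points. With a 0.5 SD change at T1–T3 in both periods it is 64/52/32% against 65/53/33% ungated, a loss of about 1 point (up to 2 in repeat runs).

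**Different scale.** Take an effect of 0.8 SD of the paired difference, with correlation 0.5 between those differences across visits. The T1 comparison alone then succeeds in 78% of trials. Behind TREATMENT it succeeds in 19% (T1 only) or 36% (halved at T2). Over 0.65–1.2 SD and correlations 0.3–0.9, the TREATMENT gate stays closed in 55–89% of trials for a T1-only effect.

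**CBI.** For an effect at one ISI at T1, with cell residual SD 1 and s shared across ISIs, the TREATMENT noncentrality is (1/12) / √[2(s² + 1/12)/20] = 0.91/0.46/0.25. TREATMENT is significant in only 14/7/6% of trials.

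**Type I error.** Under the null with a family of four, at least one false visit-level result occurs in 4.8/4.9/4.6% ungated, 1.3/1.9/2.6% behind TREATMENT, and 2.8/3.1/3.3% behind TREATMENT or the interaction. Behind any main effect, with the 0.5 SD shared change, it is 3.3/3.2/3.8%. This depends on the family: four independent uncorrected tests would give 1 − 0.95⁴ = 18.5%.

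**The case against.** The strongest reply is that the large loss belongs to one reading, and not the literal one. The sentence uses an indefinite article after models with several main effects, so on its face any main effect opens the tests. Placebo response or practice is plausible in timed tests repeated over eight visits. A shared change of that kind would open the gate nearly always and remove most of the loss. For CBI, an ordinary difference between ISIs could do the same. A factorial repeated-measures ANCOVA also normally includes the interaction, and the stated aim is the effect over time, so the authors may have meant it.

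Much of this stands. A reader might infer that the plan gates on TREATMENT, or that it leaves the interaction out of the model. The document says neither. A reader might also infer inflated Type I error. That does not follow if the Bonferroni family covers all the visit-level comparisons, but the family is not stated, so neither inflation nor its absence can be asserted without that condition.

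The reply does not remove the point. If any main effect suffices, whether real and sham are compared depends partly on changes common to both, which is a poor basis for testing treatment. If the interaction was intended, the rule does not say so.

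A further objection is that naming the gate would cure the ambiguity and that T0-adjusted contrasts go beyond it. Naming the gate is an acceptable minimum. But Bonferroni over a stated family already controls the error, so the gate can only lose power.

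**Conclusion.** The concern holds as an under-specified and ill-matched trigger for the key comparisons. For a T1-only effect, the loss against ungated testing is about 24–38 points if TREATMENT is the gate (33 − 9 to 65 − 27). It is about 10–17 points falling to about 1 if any main effect is the gate, depending on how much change both periods share. It is about 4–7 points if TREATMENT or TIME × TREATMENT is the gate. A sustained effect is hardly affected even behind TREATMENT (0–4 points).

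All sizes rest on the assumed SDs, effect, alpha and Bonferroni family. The dilution fractions, the unnamed main effect and the absence of any mention of TIME × TREATMENT do not. Carryover is a separate matter.

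**What to change.** Drop the main-effect gate. Base the conclusion on real-minus-sham contrasts at T1, T2 and T3, each adjusted for that period's T0 and Bonferroni-corrected for three comparisons. For CBI, average over ISIs first, then test by ISI. Report unregressed change from T0 as a sensitivity analysis. State alpha and the correction family.

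**Cost.** No new data and no change to conduct. For a T1-only effect the T0-adjusted contrast at 0.05/3 succeeds in 66/57/46% of trials, against 70/59/37% for unadjusted tests at the same level. That is about 4 and 2 points lower when patient-by-period variation is low, and about 9 points higher when it is high. Familywise error under the null is 4.9/5.1/4.9%. T0 regression only partly removes a systematic T0 difference. Change from T0 does not share that limit, but has only about 37% power at T1, so it suits a sensitivity analysis.

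**If a gate is kept,** name it as TREATMENT or TIME × TREATMENT, with the ISI interactions for CBI. That gate does not depend on changes shared by real and sham. It is not the least costly in every case: with a 0.5 SD shared change, the any-main-effect gate loses less. TIME × TREATMENT alone is not a good substitute, because it does worse than TREATMENT for a sustained effect.

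**If the analysis is complete,** as the past tense suggests it may be, disclose which effect served as the gate and report these contrasts regardless of it, labelled as not pre-specified.

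### Holm's step-down would give the post hoc comparisons the same family-wise control as the specified Bonferroni correction, with power at least as high, once the family of comparisons is defined

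*Combined protocol and SAP*

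**What the plan says.** The Statistical Analyses section plans a repeated-measures ANCOVA with TIME (T0 to T3) and TREATMENT (real or sham) "as within-subjects factors, and the sequence in which stimulation was performed (real-sham vs sham-real) as covariate". For cerebellar brain inhibition (CBI), ISI at 3, 5 and 10 ms is a further within-subject factor. Follow-up testing is conditional ("When a significant main effect was reached"), and the multiplicity rule for it reads: "tests with Bonferroni correction for multiple comparisons were conducted to analyze group-differences at respective ISIs or time points". No stepwise procedure is mentioned anywhere.

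The section gives no alpha level. It does not say how many comparisons make up a family, or whether T0 counts as one of them.

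The Participants section reports "Twenty-one patients with neurodegenerative ataxia" and then that "One patient with MSA-C dropped out from the study during the first round (sham stimulation) and was not considered in the present analysis", which leaves 20. It says the sample size "was assessed using a power analysis, from results obtained from previous studies", without stating any of the inputs.

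**The concern.** The primary research question asks about benefit at both short and long term. A significant omnibus result does not show whether real and sham stimulation differ at T1, T2 or T3, or at which ISI. The post hoc contrasts show that, so they carry any claim that an effect lasts.

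Single-step Bonferroni holds every contrast to alpha divided by the full number of contrasts, even after some have been rejected. Holm relaxes the threshold after each rejection, needs no assumption about dependence between contrasts, and rejects everything that Bonferroni rejects. With 20 patients, power at a later and possibly weaker time point is scarce, and some of it can be recovered within the same error bound.

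**Working it through.** **Inputs from the document.** Patients analysed: 21 − 1 = 20 (Participants). Each patient receives both treatments, so real versus sham is a paired comparison (Study design). There are four time points and three ISIs, hence up to 4 × 3 = 12 cells for CBI (Statistical Analyses).

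**Inputs assumed, because the document is silent.** Family-wise alpha 0.05, two-sided; standardised paired effect 0.3 to 1.0 SD; correlation between contrasts 0 to 0.8; number of contrasts with a true effect varied. The plan has no power figure to reproduce.

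**Rules, for m contrasts.**
- Bonferroni rejects contrast i if p_i ≤ α/m. For m = 4 the threshold is 0.05/4 = 0.0125 throughout.
- Holm orders the p-values from smallest to largest and compares the j-th with α/(m − j + 1), stopping at the first failure. For m = 4 the thresholds are 0.0125, 0.0167, 0.025 and 0.05.

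The first threshold is the same under both rules and the later ones are larger under Holm. So Holm never rejects less, and any gain comes after the first rejection.

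**Single-test power.** For a paired t-test with noncentrality 0.66 × √20 = 2.95 and 19 degrees of freedom, power is 79.9% at 0.05, 63.1% at 0.05/3 and 58.4% at 0.05/4.

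**Simulated average power per true comparison.** n = 20, m = 4, 20,000 trials per setting. Correlation is 0.5, except in the two-effect row, where it is 0.3 and 0.6.

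| Time points with an effect | Effect (SD) | Bonferroni | Holm | Gain (points) |
|---|---|---|---|---|
| 1 | 0.66 | 58.5% | 58.5% | about 0.1 |
| 2 | 0.66 | about 58% | about 61% | just under 3 |
| 3 | 0.66 | 57.9% | 63.9% | 6.0 |
| 3 | 0.3 | 10.4% | 11.6% | 1.2 |

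**Other families.**
- Three contrasts (T1, T2, T3), all with 0.66 SD: a gain of about 9 to 10 points. With only one of the three non-null, it is 0.0 to 0.2.
- Twelve CBI cells at 0.66 SD and correlation 0.5: 40.9% to 47.6% with nine cells non-null, and 41.1% to 42.4% with three.
- Over every setting tried, the gain ran from 0 to about 19 points. The top value needs all twelve cells non-null.

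**Chance of detecting at least one true effect.** With three of four time points at 0.66 SD and correlation 0.5, it is 82.5% under both methods. The difference was 0.2 points or less in every setting.

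**False positives.** With no true effects, the simulated family-wise error was identical for the two methods (0.040 to 0.050). With three of four time points at 0.66 SD, the null contrast was rejected about 1.3% of the time under Bonferroni and roughly 3% to 3.6% under Holm. Holm's error stayed at or below 5% in all settings.

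**Effect of the family itself.** If T0 is counted, each contrast at 0.66 SD starts from 58.4% power; if it is not, from 63.1%. The difference, 63.1 − 58.4 = 4.7 points, is of the same order as the Holm gain.

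**The case against.** The strongest reply is that nothing here is wrong. Bonferroni after a significant omnibus test is legitimate, does not inflate type I error, and comes with simple simultaneous confidence intervals. That stands, and it is why the point is optional.

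A reader might infer that Bonferroni costs this trial about 6 points of power per comparison. The documents do not support that. They give no effect size, alpha, correlation or family size, and 6 points appears only when most of the contrasts carry a moderate effect. If the effect fades after T1, which is possible in a trial that asks about durability, the gain is close to nil. The calculations also left out the omnibus gate and the sequence covariate, so they are not this trial's actual post hoc power.

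A reader might also infer that Holm is free of any cost in error. The 5% bound is unchanged, but the actual false-positive rate rises towards it. In addition, a Bonferroni interval can include zero where Holm declares a difference.

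Two practical objections also stand. Changing one word is not enough, because Holm's steps are as undefined as Bonferroni's divisor until the family is stated. And the text is in the past tense with a dropout already excluded, so results may be known; replacing the specified method with a less conservative one at that stage would be open to criticism.

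These objections change the wording and the fix. They do not remove the gain.

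**Conclusion.** The point holds as an optional efficiency improvement. That Holm has the same strong family-wise control and is never less powerful is a mathematical property that depends on no trial input.

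The size of the gain does depend on inputs. For four time points it is about 0 points with one true effect, about 3 with two and about 6 with three (each at 0.66 SD), and about 1 with three effects of 0.3 SD. This assumes 20 paired patients and two-sided family-wise alpha 0.05. None of these figures is a property of the trial as documented. The benefit lies in declaring a second or later time point, not in finding any effect at all.

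It would be too strong to say that the post hoc analysis is invalid or that the omnibus ANCOVA is weakened. The choice of correction does not touch the omnibus test, and Bonferroni keeps the family-wise error within its bound.

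**What to change.** 1. State alpha and which comparisons form the family within each outcome. For example: real versus sham at T1, T2 and T3 for the clinical scores, and the time-by-ISI cells for CBI. State whether T0 is included.
2. Replace 'Bonferroni correction' by 'Holm step-down correction' for those comparisons.
3. Report unadjusted or Bonferroni intervals beside the Holm-adjusted p-values, say which they are, and note that a Bonferroni interval may not match a Holm decision.
4. If results are already known, keep the specified Bonferroni result, report Holm beside it, and label it as added later.

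The cost is a sentence or two in the analysis section and a hand calculation from the unadjusted p-values, with no new data. The downsides are the lack of simple matching simultaneous intervals and a higher actual false-positive rate that stays within the 5% bound.

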CBI was assessed using previously described techniques ¹⁵⁻¹⁷. Briefly, the second coil was used to deliver the conditioning stimuli (CS) which was placed over the contralateral cerebellar hemisphere ¹⁸ (1 cm inferior and 3 cm right to the inion), a site corresponding to the posterior and superior lobules of the lateral cerebellum ¹⁹. For cerebellar stimulation, the handle was positioned upward with the coil placed tangentially to the skull (see **Fig. 1**). The cerebellar CS intensities were set at 90% rMT obtained in the ipsilateral motor cortex ¹⁷. CS preceded the target stimuli (TS) by different interstimulus intervals (ISIs) ranging from 3 to 10 ms (3, 5, 10 ms). There were four conditions, corresponding to the three different ISI and the TS alone. Ten responses were collected for each different ISI and fifteen for the TS alone in a pseudorandomized sequence. The amplitude of the conditioning MEPs was expressed as a ratio of the mean unconditioned response. The inter trial interval was set at 5 sec ($\pm 10\%$).

Transcranial direct current stimulation

tDCS was delivered by a battery-driven constant current stimulator through a pair of saline-soaked (0.9% NaCl) surface sponge electrodes ($7 \times 5 \text{ cm}^2$, current density 0.057 mA/cm^2 for the anodal cerebellar electrode; $8 \times 6 \text{ cm}^2$, current density 0.041 mA/cm^2 for the cathodal spinal electrode). The anode was placed on the scalp over the cerebellum area (2 cm under the inion) and the cathode over the spinal lumbar enlargement (2 cm under T11) (see **Fig. 1**). The electrodes were secured using elastic gauzes and an electroconductive gel was applied to electrodes to reduce contact impedance ($<5 \text{ k}\Omega$ for all sessions).

During anodal stimulation a constant current of 2 mA was applied for 20 minutes, as suggested by recently published consensus recommendations^{20,21} and on the basis of computation modeling studies.^{22,23}

For the sham condition, the electrode placement was the same, but the electric current was ramped-down 5 seconds after the beginning of the stimulation to make this condition indistinguishable from the experimental stimulation. To detect differences in the perception of the stimulation, we asked the patients whether they thought they were receiving real or sham stimulation at the end of the two-weeks' treatment.

Statistical Analyses

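### Do the Spearman correlations need a multiplicity correction or an exploratory label written into the plan?

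*Combined protocol and SAP*

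**What the plan says.** The correlations get one sentence in Statistical Analyses: Spearman "rank-order correlations were used to assess associations between the improvement in functional scores, neurophysiological parameters and demographic or clinical characteristics". That sentence names three groups of variables. It does not name pairs, a visit, a treatment period, a definition of improvement, a significance level, an adjustment or an inferential status, and no other section supplies these.

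The one multiplicity provision is in the preceding paragraph. It opens with "When a significant main effect was reached" and provides that post hoc "tests with Bonferroni correction for multiple comparisons were conducted to analyze group-differences at respective ISIs or time points". A correlation has no main effect and is not a group difference at an interval or visit, so the clause does not reach it.

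The supply of variables is as follows. Clinical assessment lists SARA, ICARS, the 9-hole peg test timed separately for each hand, the 8-metre walk and the SF-36. For cerebellar brain inhibition (CBI), "There were four conditions, corresponding to the three different ISI and the TS alone". Study design sets three visits after baseline in each of the two cross-over periods.

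The primary research question is whether stimulation "could improve symptoms and modulate cerebello-cerebral connectivity in patients with ataxia, at short and long-term". Two repeated-measures ANCOVAs, one for clinical scores and one for CBI, compare real with sham stimulation to answer it.

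**The concern.** The plan corrects its post hoc contrasts but is silent on a more open-ended set of tests. A reader could assume a protection that is absent. The correlations are also the only analysis that sets clinical change beside CBI change, so one nominally significant coefficient could be presented as evidence that benefit runs through cerebello-cerebral connectivity. With many possible pairs and few patients, such a coefficient can easily arise by chance.

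A second worry concerns the undefined improvement. The plan does not say that it is net of the same patient's change under sham. If both variables entered as raw change in the real period, a non-specific response common to both could produce a correlation without any stimulation effect.

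**Working it through.** The plan states no error rate, test count or power for the correlations, so there is no figure of its own to reproduce. The following shows how large the issue could be.

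**Inputs**
- Patients analysed: 21 − 1 drop-out = 20 (Participants), so 18 degrees of freedom.
- Significance level: not stated; 0.05 two-sided per test is assumed.
- Number of tests, m: not stated; two assumed grids at one visit. (a) SARA, ICARS, peg test for each hand and 8-metre walk by three intervals: 5 × 3 = 15. (b) SARA and ICARS by three intervals: 2 × 3 = 6.

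**Coefficient needed for significance.** |r| = t / √(18 + t²), with t the two-sided critical value on 18 degrees of freedom.
- At 0.05: t = 2.101, so |r| = 2.101 / √22.41 = 0.444.
- At 0.05/6 = 0.0083: t = 2.963, |r| = 0.573.
- At 0.05/15 = 0.0033: t = 3.380, |r| = 0.623.

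**Chance of at least one false association, no correction.** For independent tests this is 1 − 0.95^m:
- m = 6: 1 − 0.735 = 0.265.
- m = 15: 1 − 0.463 = 0.537.

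Clinical scores correlate with each other, and so do the CBI intervals. The table gives simulated rates for 20 patients, with Spearman's coefficient tested by the t approximation, no true association between the two sets, and equal correlation within each set.

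| Correlation within each set | 15 tests | 6 tests |
|---|---|---|
| 0 | 0.54 | 0.27 |
| 0.5 | 0.43 | 0.23 |
| 0.7 | 0.33 | 0.19 |
| 0.8 | 0.27 | 0.17 |

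At the first Holm step the corresponding rates are 0.035 to 0.060 (15 tests) and 0.039 to 0.056 (6 tests).

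The count drives the answer. Adding one SF-36 score gives 6 × 3 = 18 tests and 1 − 0.95^18 = 0.60 if independent. Taking all three follow-up visits gives 54 tests and 0.94. At 18 tests, a within-set correlation of 0.9 brings the rate down to 0.19. The documents do not fix any of these counts.

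**What correction would cost.** Power to detect one true correlation (bivariate normal, 20 patients):

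| True correlation | Uncorrected | First Holm step, 6 tests | First Holm step, 15 tests |
|---|---|---|---|
| 0.5 | 0.58 | 0.30 | 0.20 |
| 0.6 | 0.77 | 0.51 | 0.39 |
| 0.7 | 0.92 | 0.75 | 0.64 |

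**What one coefficient can say.** For a Spearman coefficient of 0.60, Fisher's z is 0.693 with standard error √((1 + 0.6²/2)/17) = √(1.18/17) = 0.263. The 95% interval is 0.693 ± 1.96 × 0.263 on the z scale, or 0.17 to 0.84 transformed back. An interval that wide shows how little one coefficient settles, whether or not a p-value is attached.

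**The case for a change.** The strongest case for a change is that even the mildest setting examined for the two grids, six tests with strongly correlated outcomes, gives about 17%, more than three times 0.05. Under 15 tests, a coefficient between 0.44 and 0.62 would be nominally significant yet fail the first Holm step. The remedy would be wording only: either list the pairs at one visit and apply Holm, or call the analysis exploratory and report every coefficient with its interval.

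The arithmetic stands, and so does the reading of the Bonferroni clause. The step from there to a needed change does not.

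- **No rule is being broken.** The correlation sentence sets no significance threshold and claims no test. A family-wise rate matters only if someone later declares significance, and its size depends on counts that the documents do not give.
- **Holm at one visit is a debatable trade.** It nearly halves power at a correlation of 0.6 with 15 tests, and it leaves the other visits untested although the research question covers both short and long term. It may also be unavailable: the text is in the past tense and already reports the drop-out, so naming a visit in advance is doubtful.
- **An exploratory label and a definition of improvement** would be good reporting. They write down what is unsaid and change no estimate.
- **The shared-response worry is not supported by the documents.** Patients and the examiners doing the ratings and TMS were blinded, and nothing suggests a common non-specific response in an amplitude ratio from TMS. Because "each patient received the opposite treatment (cross-over phase), and underwent the same standarized assessment as in the first phase", a sham-subtracted correlation is possible. It would be noisier, with a standard deviation up to √2 = 1.41 times that of the raw change, and it would need adjustment for sequence. That is an optional extra.

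**Conclusion.** No change to the plan is called for. The plan leaves unsaid how many correlations are run, at which visit and period, and how improvement is measured, and its Bonferroni clause does not cover them. At an assumed 0.05 per test in 20 patients, the uncorrected chance of at least one false association is about 17% to 27% for 6 tests and 27% to 54% for 15. These ranges assume the two grids and within-set correlations from 0 to 0.8.

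This is an unwritten convention for a secondary association analysis. The ANCOVAs that answer whether stimulation improves symptoms and modulates CBI are untouched, and the research question does not ask whether one change tracks the other. Analysts can fill the gap sensibly at the reporting stage by treating the coefficients as hypothesis-generating and stating how many were computed. A formal correction would buy error control for a claim the plan does not make, at a large cost in power. The view would change only if a correlation were offered as confirmatory evidence of mechanism.
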